4.1.7.2. Adherence to Study Treatment

Summary of prematurely discontinuing study treatment (including reason for discontinuation) will be provided by study treatment. A time-to-event analysis of premature study treatment discontinuation will also be conducted.

If data warrants, the counts and percentages of participants who follow the planned escalation scheme, have dose interruption, or have dose de-escalation will be summarized for the tirzepatide treatment group. This will include the percentage of participants who have 10 mg or 15 mg tirzepatide as their MTD. In addition, the proportion of participants receiving 2.5, 5, 7.5, 10, 12.5, or 15 mg may be presented by randomized tirzepatide treatment and visit during the dose escalation period.

Treatment adherence will be defined as taking at least 75% of the scheduled tirzepatide doses. Treatment adherence will be summarized descriptively over the treatment period by treatment using the mITT population.

4.1.8. Important Protocol Deviations

Important protocol deviations are identified in the Trial Issues Management Plan. A listing and a summary of important protocol deviations by treatment will be provided.

4.2. Participant Dispositions

The participant dispositions for the screening period, the study intervention/treatment period, and/or the follow-up period will be collected in CRFs with the corresponding primary reason. The study completion for a participant is defined as the participant completing both the treatment period and the follow-up period, regardless of completion of study treatment.

Summaries and a listing of study disposition and study drug disposition will be provided for all randomized participants, separately for each ISA. Comparison between treatment arms will be performed using Fisher's exact test.

4.3. Primary Endpoint Analysis

The primary objective of this study is to test the hypothesis that tirzepatide at the MTD (10 mg or 15 mg) is superior to placebo for participants with moderate to severe OSA and obesity on the mean AHI reduction from baseline to Week 52. The primary and key secondary efficacy analyses will be guided by 2 estimands, the "treatment regimen" estimand and the "efficacy" estimand to support global regulatory submissions and publications.

4.3.1. Analysis Related to the Efficacy Estimand

The primary analysis guided by the "efficacy" estimand will be conducted using the EAS. This analysis will be based on the contrast between tirzepatide at the MTD (10 mg or 15 mg) and placebo at Week 52 (Visit 11) from the MMRM analysis of mean change from baseline in AHI. All the longitudinal observations at each scheduled postbaseline visit will be included in the analysis. REML will be used to obtain model parameter estimates and the Kenward-Roger option will be used to estimate the denominator degrees of freedom. The response variable of the MMRM will be the change in AHI from baseline values obtained at each scheduled postbaseline AHI measurement.

The model will include the fixed class effects of treatment, strata (geographic region [US/OUS] and gender), visit, and treatment-by-visit interaction, as well as the continuous, fixed covariate of baseline AHI. An unstructured covariance structure will be used to model the within-participant errors. Significance tests will be based on least squares means and Type III tests. If this analysis fails to converge, the following covariance structures will be tested in order until convergence is achieved:

- Toeplitz with heterogeneity
- autoregressive with heterogeneity
- compound symmetry with heterogeneous variances
- Toeplitz
- autoregressive, and
- compound symmetry without heterogeneous variances.

Analysis aligned to each estimand will be evaluated at the full significance level of 0.05.

4.3.2. Analysis Related to the Treatment Regimen Estimand

For the primary analysis guided by the “treatment regimen” estimand, the analysis will be conducted using the FAS. Missing values will be imputed based on the strategy to handle intercurrent events described in Section 4.1.2. After imputation, the primary efficacy comparison will be based on the contrast between tirzepatide at the MTD (10 mg or 15 mg) and placebo from the ANCOVA analysis of mean change from baseline to Week 52 in AHI using FAS. The ANCOVA model will include treatment and strata (geographic region [US/OUS] and gender) as fixed effects and baseline AHI as a fixed covariate. Statistical inference over multiple imputed data sets will be guided by Rubin (1987).

4.3.3. Sensitivity Analyses

For participants in ISA2, a sensitivity analysis will be carried out for the primary endpoint. When carrying out this sensitivity analysis using a treatment regimen estimand, participants with PAP withdrawal less than 5 days before the PSG at baseline or at Week 52 will have their data censored. Censored postbaseline data will be imputed using the approach outlined in Section 4.1.2. An ANCOVA model will be fit using the approaches outlined in Section 4.3.2. Carrying out this sensitivity analysis using the efficacy estimand, observations made with PAP withdrawal less than 5 days prior to PSG from the MMRM will be censored. Additional sensitivity analyses for ISA2 participants to accommodate participants with PAP withdrawal <5 days prior to the PSG may be considered.

Additional sensitivity analyses for both ISAs may be included as needed.

4.4. Secondary Endpoints Analysis

4.4.1. Key Secondary Endpoints

A graphical approach for multiple comparisons will be used to strongly control the overall Type 1 error (2-sided alpha level of 0.05) for testing the superior treatment effect of tirzepatide MTD over placebo including the key secondary endpoints as listed below.

- percent change in AHI at Week 52
- percent of participants with $\geq 50\%$ AHI reduction at Week 52
- percent of participants at Week 52 with
 - AHI <5 or
 - (AHI 5 through 14 and ESS ≤ 10)
- percent change from baseline to Week 52 in body weight
- change from baseline to Week 48 in SBP
- change from baseline to Week 52 in C-reactive protein (high-sensitivity C-reactive protein)
- change in sleep apnea-specific hypoxic burden (% minutes/hour)
- change in PROMIS Sleep-related impairment short form 8a, and
- change in PROMIS Sleep disturbance short form 8b.

Analytical approaches for the hierarchical assessment of PROs are described in Section 4.4.3.1 and a summary of the analysis approach for all other key secondary endpoints is provided in Section 4.4.1.1.

4.4.1.1. Main Analytical Approaches

Analysis of percent change in AHI, percent change from baseline to Week 52 in body weight, change from baseline to Week 52 in log of high-sensitivity C-reactive protein, change from baseline to Week 48 in SBP, change from baseline to Week 52 in PROMIS Sleep-related impairment, change from baseline to Week 52 in PROMIS Sleep disturbance, and change from baseline to Week 52 in log of hypoxic burden will be conducted in a manner similar to the primary efficacy analyses using an ANCOVA model with treatment, strata (geographic region [US/OUS], AHI stratum [not severe (AHI <30), severe (AHI \geq 30)], and gender), and baseline of the corresponding variable as a covariate for the treatment regimen estimand. If the hypoxic burden is reported to be 0, log (1) will be used in place of the log of hypoxic burden. The analysis method utilizing data from both ISAs for change from baseline to Week 52 in PROMIS sleep Impairment and PROMIS Sleep disturbance is described in the integrated efficacy analysis plan.

For the efficacy estimand, the MMRM analyses will be conducted as described in Section 4.1. For both estimands, analysis of percent change in AHI will adjust for the continuous, fixed baseline value of AHI instead of the baseline AHI stratum (not severe, severe).

Comparisons at the 52-week visit between the treatments relative to the proportion of participants achieving \geq 50% AHI reduction and AHI <5 or (AHI 5 through 14 and ESS \leq 10) will be conducted using logistic regression analysis including the following terms as a covariate:

- treatment
- geographic region (US/OUS)
- baseline AHI, and
- gender.

Unconditional risk differences will also be provided for these endpoints using logistic regression (Ye et al. 2023).

Analysis aligned to each estimand will be evaluated at the full significance level of 0.05 contingent on reaching statistical significance of the primary objective.

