| | | 
Section 4.1:
 
 Added language on baseline AHI. Modified the postbaseline definition for PRO measures. Updated that geographic region will be used in lieu of pooled country as a covariate in analysis models. Changed AHI groups to be included in the model as covariates. | 
 Language added for clarification. Updated to clarify the definition. Changed to reduce the number of strata in the model and to keep enough participants in each covariate strata. Changed the group category from “moderate” to “not severe” to incorporate inadvertently enrolled participants. |

| SAP Version | Approval Date | Change | Rationale |
|-------------|---------------|---|---|
| | | 
Section 4.1.2:
 
 Updated missing data and imputation method in Table GPIF.4.2. | 
 Missing data imputation algorithm revised, in part to include inadvertent enrollees in analysis, and language on missing data clarified per FDA feedback. |
| | | 
Section 4.1.2:
 
 Added no OSA and mild categories to baseline OSA category | 
 Added to account for inadvertently enrolled patients |
| | | 
Section 4.1.6:
 
 Added definition for baseline and postbaseline concomitant medication use. | 
 Clarified definition for related tables and listings. |
| | | 
Section 4.2:
 
 Added definition for participant study disposition. | 
 Clarified the definition of participant study disposition based on collected CRF data. |
| | | 
Section 4.4.1.2:
 
 Added analysis for change in log hypoxic burden. Added reporting of unconditional risk difference from logistic regression. | 
 Log scale is deemed appropriate for analysis as the measure is an area under the curve. Added to provide additional measure of treatment effect in accordance to FDA guidance. |

| SAP Version | Approval Date | Change | Rationale |
|-------------|---------------|---|--|
| | | Section 4.6: 
 Added hepatobiliary events, malignancies, and abuse potential as special safety topics. | 
 Updated to provide information on special safety topics. |

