1.1. Objectives, Endpoints, and Estimands

| Objective | Endpoints |
|--|--|
| Primary | |
| To demonstrate that tirzepatide at the MTD (10 mg or 15 mg) QW is superior to placebo for decrease in AHI. | Change in AHI from baseline to Week 52. |
| Key Secondary (controlled for Type 1 error) | |
| To demonstrate that tirzepatide at the MTD (10 mg or 15 mg) QW is superior to placebo for | From baseline to Week 52 |
| Percent change in AHI | Percent change in AHI |
| Clinically meaningful change in AHI | Percent of participants with $\geq 50\%$ AHI reduction |
| Achieving OSA remission or mild non-symptomatic OSA | Percent of participants with AHI < 5 or AHI 5-14 with ESS ≤ 10 |
| Change in body weight | Percent change in body weight |
| Change in inflammatory status | Change in hsCRP concentration |
| Hypoxic burden | Change in SASHB (% min/hour) |
| Change in PROs | Change in ^a : PROMIS Sleep-related impairment short form 8a PROMIS Sleep disturbance short form 8b |
| Change in SBP | From baseline to Week 48 ^b Change in SBP |
| Other Secondary | |
| To demonstrate that tirzepatide at the MTD (10 mg or 15 mg) QW is superior to placebo for | From baseline to Week 52 |
| Change in excessive daytime sleepiness | Change in ESS score |
| Change in patient-reported functional status as assessed by FOSQ (30 items) | Change in FOSQ-10 score Change in FOSQ (30 items) Score Change in all FOSQ domain scores, specifically General Productivity Activity level Vigilance Social outcomes Intimate and sexual relationships |
| Change in body weight | Percent of participants who achieve $\geq 10\%$ body weight reduction $\geq 15\%$ body weight reduction $\geq 20\%$ body weight reduction |
| Change in lipid parameters | Change in HDL-cholesterol non-HDL-cholesterol triglycerides |

| Objective | Endpoints |
|---|---|
| A hierarchical assessment of PRO change | A hierarchical combination of the following: Change in PROMIS Sleep-related impairment short form 8a Change in PROMIS Sleep disturbance short form 8b |
| Change in supportive secondary PROs | Change in: SF-36v2 acute form domain and summary scores Percent of participants with improved categorical shift in: PGIS-OSA Sleepiness PGIS-OSA Fatigue PGIS-OSA Snoring Proportion of participants achieving clinically meaningful within-patient change in: PROMIS Sleep-related impairment PROMIS Sleep disturbance |
| Insulin Change in DBP | Change in fasting insulin From baseline to Week 48 ^a Change in DBP |
| Exploratory | |

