4.4.1.2. Sensitivity Analyses

For participants in ISA2, sensitivity analyses for the key secondary endpoints will be carried out: percent change in AHI, clinically meaningful change in AHI, and achieving OSA remission/mild nonsymptomatic OSA.

For percent change in AHI, the sensitivity analysis using both the treatment regimen and efficacy estimand will be carried out. When using a treatment regimen estimand approach, participants with PAP withdrawal less than 5 days before the PSG at baseline or at Week 52 will have their data censored. Censored postbaseline data will be imputed using the approach outlined in

Section 4.1.2. An ANCOVA model will be fit using the approaches outlined in Section 4.3.2. When using the efficacy estimand, observations made with a PAP withdrawal less than 5 days prior to the PSG or PROMIS from the MMRM will be censored.

For the binary endpoints of clinically meaningful change in AHI and achievement of OSA remission/mild nonsymptomatic OSA, the sensitivity analysis using both estimands will be carried out. PSG measurements taken after <5 days of PAP withdrawal will be censored. After censoring, analysis will be carried out as described in Section 4.4.1.1.

Additional sensitivity analyses for ISA2 participants to accommodate participants with PAP withdrawal <5 days prior to the PSG or PROMIS or ESS may be considered.

A 2-way tipping point analysis may also be utilized for the primary endpoint. This analysis will begin with the primary analysis aligned to the treatment regimen estimand and then adding positive and negative penalties simultaneously to both the tirzepatide MTD arm and the placebo arm, considering when results tip from superiority to inconclusive, and then considering the clinical plausibility of such scenarios.

Additional sensitivity analyses for both ISAs may be included as needed.

4.4.2. Type 1 Error Rate Control Strategy for Primary and Key Secondary Efficacy Analyses

All primary and key secondary hypotheses will be tested with the overall family-wise Type 1 error rate at a 2-sided alpha level of 0.05 through the multiplicity control approach based on the graphical multiple testing procedure. The primary endpoint hypothesis will be tested at a 2-sided alpha level of 0.05 for statistical significance. If the primary efficacy endpoint is significant, the alpha of 0.05 will be propagated to the key secondary efficacy endpoints. The detailed graphical testing scheme is outlined in Figure GPIF.2.1.

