4.9. Changes to Protocol-Planned Analyses

Refer to [Table GPIF.1.1](#).

5. Sample Size Determination

Approximately 206 participants per ISA will be randomly assigned to either tirzepatide or placebo in a 1:1 ratio (approximately 103 participants per treatment arm), and the statistical power will be evaluated for the primary efficacy endpoint and key secondary combination PRO endpoint at a 2-sided significance level of 0.05. This sample size will provide the following:

- at least 90% power to demonstrate superiority of tirzepatide at the MTD (10 mg or 15 mg) to placebo for the mean percent change from baseline in AHI, assuming 50% improvement, with a common standard deviation of 50% and a dropout rate of 25%, and
- at least 90% power to demonstrate superiority of tirzepatide at the MTD (10 mg or 15 mg) to placebo for the hierarchical combination PRO endpoint using the Finkelstein-Schoenfeld method (Finkelstein and Schoenfeld 1999), with a dropout rate of 25%.

An upper limit of approximately 70% enrollment of male participants will be used to ensure a sufficiently large sample of female participants.

6. Supporting Documentation

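### The zero rule for log hypoxic burden scores 0 as worse than any reported value between 0 and 1; one sentence flooring all values at 1 removes this minor flaw

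*SAP*

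**What the plan says.** SAP Section 1.1 lists hypoxic burden, in % min/hour, among the key secondary endpoints controlled for Type 1 error, and Section 4.4.1 repeats it. Under Section 4.4.2 the primary and key secondary hypotheses are tested with the "overall family-wise Type 1 error rate at a 2-sided alpha level of 0.05".

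Section 4.4.1.1 defines the analysed variable as "change from baseline to Week 52 in log of hypoxic burden". It is analysed by ANCOVA for the treatment regimen estimand and by MMRM for the efficacy estimand. The same section gives the zero rule: "If the hypoxic burden is reported to be 0, log (1) will be used in place of the log of hypoxic burden".

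The version history justifies the transformation: "Log scale is deemed appropriate for analysis as the measure is an area under the curve". It does not explain the choice of log(1) for zeros. Neither document gives a floor, an offset or a detection limit for positive values below 1. The sensitivity analyses named in Section 4.4.1.2 concern AHI-based endpoints, and beyond those the section only leaves room for more if needed.

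**The concern.** A lower hypoxic burden is better, so any scoring of it should never give a lower value a worse score. The stated rule does. It moves 0 up to the score of 1 and leaves everything between 0 and 1 on its original negative log. The best possible result then scores the same as 1 and worse than every value strictly between 0 and 1.

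The flaw can also act at baseline. Version 3 of the SAP brings inadvertently enrolled participants into the analysis, and Section 4.1.5 adds a baseline category of AHI below 5, so very low baseline values are possible. A participant who went from 0.2 to 0 would be recorded as having worsened.

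At stake are the size and reading of the estimate on an error-controlled endpoint. None of the named sensitivity analyses would show how far that estimate depends on the rule.

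**Working it through.** The documents state no effect size, SD or power for hypoxic burden, so there is no planned figure to reproduce.

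**Step 1: the scoring rule.** From SAP 4.4.1.1, f(0) = log(1) = 0 and f(x) = log(x) for x > 0. With natural logs:

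| SASHB | Score as stated | Score with floor at 1 |
|---|---|---|
| 0 | 0 | 0 |
| 0.1 | -2.30 | 0 |
| 0.2 | -1.61 | 0 |
| 0.5 | -0.69 | 0 |
| 1 | 0 | 0 |
| 2 | 0.69 | 0.69 |

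The stated column is not monotone. The direction is the same for any log base above 1.

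**Step 2: one participant.** Assume a baseline of 100, with log 4.605.
- Week 52 value of 0: change 0 - 4.605 = -4.605, read as a 99.0% reduction.
- Week 52 value of 0.2: change -1.609 - 4.605 = -6.215 (unrounded logs), read as a 99.8% reduction.

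Complete resolution is scored 1.609 log units worse. For a baseline of 0.2 and a Week 52 value of 0, the change is 0 - (-1.609) = +1.609, a recorded worsening.

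**Step 3: size of the shift against a floor at 1.** Zeros score 0 under both rules, so the two estimates differ only through values strictly between 0 and 1. All distributions below are assumed.

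*Scenario A.* 77 per arm (103 × 0.75, using the planned arm size and dropout), placebo median 60, log-SD 1.0, log difference -0.5, and sub-1 values uniform on 0.1 to 1. The mean log of such a value is [(-1) - (0.1 × (-2.303) - 0.1)] / 0.9 = -0.670 / 0.9 = -0.744. The expected shift is the between-arm difference in the share of such values, times -0.744. The share of zeros was set equal to the share of sub-1 values in each arm.

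| Sub-1 share, tirzepatide v placebo | Expected shift | Simulated estimate, stated v floor | Simulated power, stated v floor |
|---|---|---|---|
| 2% v 0% | 0.02 × -0.744 = -0.015 | -0.660 v -0.645 | 95.8% v 95.7% |
| 5% v 1% | 0.04 × -0.744 = -0.030 | -0.808 v -0.778 | 96.1% v 96.4% |
| 10% v 2% | 0.08 × -0.744 = -0.060 | -1.111 v -1.051 | 99.0% v 99.1% |

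The simulation (4,000 replicates) agrees with the arithmetic.

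*Scenario B, extreme.* 103 per arm, log-SD 1.3, medians 60 v 5, and on tirzepatide 10% zeros with 11% of non-zero values below 1. Estimates were -2.61 (stated) v -2.55 (floor), with z -14.0 v -14.2. A separate run gave -2.64 v -2.58. The gap is 0.06 both times.

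*Scenario C, burden halved.* As B, but with a tirzepatide median of 30 and 2% zeros. About 0.4% of tirzepatide values fall below 1, roughly 103 × 0.004 = 0.4 of a participant. Estimates were -0.762 v -0.760, z -4.11 under both rules, and power 97.8% v 97.9%.

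**Step 4: Type I error.** With no treatment difference and 4,000 replicates, the stated rule rejected in 4.8% of trials (both medians 5, 10% zeros) and in 5.5% (both medians 60, 2% zeros). The floor also gave 5.5% in the second case. The Monte Carlo standard error is √(0.05 × 0.95 / 4000) = 0.34 percentage points, so both rates are compatible with 5%.

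**The case against.** The strongest reply is that the reversal may never occur. It needs reported values strictly between 0 and 1, and nothing in the documents shows that any will exist. If SASHB is reported in whole numbers, the rule is monotone, 0 ties with 1, and it is identical to a floor at 1. Entry requires AHI of at least 15, with hypopneas scored only at 4% desaturation or more, so near-zero baselines should be rare. Even the extreme scenario leaves the test result unchanged. All of this stands, and it is why the point is conditional and minor. It does not rescue the rule, because the documents do not exclude such values and the stated scoring is wrong wherever they occur.

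A reader might infer three stronger things that the documents do not support.

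- *That the error control is compromised.* The rule is the same in both arms, and the null simulations show no inflation.
- *That the rule distorts a true ratio of geometric means.* With zeros present, a geometric mean has no value until a convention is chosen, so there is no true ratio to depart from. The direction of the shift depends on the comparator: at 10% v 2% in Scenario A the stated rule gives -1.11, a floor at 1 gives -1.05, and replacing 0 by half of an assumed minimum of 0.1 gives -1.35.
- *That log(SASHB + 1) is an equally good repair.* It moves the estimate more than the flaw does: -2.41 against -2.64 (stated) and -2.58 (floor) in Scenario B, and -0.731 against -0.762 and -0.760 in Scenario C. It also loses the simple ratio reading.

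**Conclusion.** The rule is wrong as written: it gives complete resolution a worse score than any value strictly between 0 and 1, on a Type 1 error-controlled key secondary endpoint. Whether this affects any participant depends on the distribution and reporting precision of SASHB, which the documents do not give.

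Under the assumed distributions, the estimate moves by at most about 0.06 on the natural-log scale compared with a floor at 1. Power moves by about 1 percentage point or less, and Type I error is not inflated. A materially larger share of values below 1, or a larger imbalance between arms, would move the estimate further in proportion. The point is minor, and worth correcting because the correction is so cheap.

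**What to change.** Replace the zero-rule sentence in SAP Section 4.4.1.1 with: *hypoxic burden values below 1, including 0, will be set to 1 before log transformation*. That is log(max(SASHB, 1)). State that it applies to all baseline and post-baseline values, and alike in the ANCOVA, the MMRM and the imputation model.

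This keeps the sponsor's own log(1) for zeros, restores the ordering (with ties below 1), and changes nothing if no values fall between 0 and 1. The cost is one sentence, with no extra data collection. The small downside is that distinctions below 1 are lost. The change belongs before the first ISA is unblinded, which is when Section 4.1 requires the SAP to be final.
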